## Phase II R – Responders Long-Term Response

## Appendix B

Event	Post Treatment Follow Up Phase (7.5 Months)					
	Phone Visit (Clinic Optional)	Phone Visit (Clinic Optional)	Phone Visit (Clinic Optional)			
Week	46	56	68			
Visit Number	22	25	28			
Voiding Diary (VOID) (24 hour)	X 	X 	X 			
Patient's Daily Medication Diary (PTDIARY)			Х2			
Concomitant Medication (CMED)			X			
Serious Adverse Event (SAE)	X	X	X			
Study Stop Point II R (SSTOPIIR)			X 			
Study Close-out (STCL)			X³			
SYMPTOM QUESTIONNAIRES:						
Follow-up Symptoms (FUSYM)	X	X	Х			
IC Symptom & Problem Index (SYMPROB)	Х	X	Х			
U. of Wis. Symptom Survey (UNIVWIS)	Х	X	X			

 $X^1$  = Voiding Diaries handed out at week 34.

 $X^2$  = Patient Daily Med Diary handed out at Week 34. Patient instructed to begin filling out at week 65.

 $X^3$  = When indicated.

Page 4 of 4 05/28/02

## APPENDIX C

## PROTOCOL FOR THE ADMINISTRATION OF BCG

#### I. Pre-Instillation

#### A. Initial Visit for First Instillation:

- 1. Upon presentation to office, the pharmacy is contacted to reconstitute and prepare solution.
- 2. Position patient in lithotomy and prepare skin and genitalia in a standard manner with antiseptic solution
- 3. Prepare for catheterization (lubrication, etc.).
- 4. Perform urethral catheterization.
- 5. Dipstick urine for nitrites.
- 6. If nitrites are absent, proceed with instillation. (GO TO NEXT SECTION: **Instillation of Solution**).
- 7. If nitrites are present on dipstick analysis, perform microscopic examination of urine. If microscopic examination reveals bacteria, consider empiric antibiotic therapy for bacterial UTI. Perform urine culture and postpone instillation pending results of urine culture. In 24-48 hours, the urine culture results will be available. If the urine culture is negative, proceed with instillation. If the urine culture is positive, complete antibiotic therapy and proceed with instillation after UTI is appropriately treated.

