### 10.3.1 Treatment Visit I

756 757

The study coordinator or investigator will review any clinical problems or events occurring since last study contact and update the concomitant medications record with any changes in medication use.

759 760 761

762

763

764

765

766

758

**Safety Assessment**: Female patients will be asked the date of their last menstrual period. An assessment of current birth control methods will be performed and recorded in the patient's chart and Case Report Form (CRF), if appropriate. For women of child-bearing potential, if pregnancy is suspected, a repeat β-HCG pregnancy test will be performed. If a repeat pregnancy test is performed and the results are positive, treatment should be discontinued immediately and the patient should be discontinued from the study and the Clinical Center Stop Point or "STOP" CRF should be filled out.

767 768 769

770

771

Prior to administering the first study treatment, a urine specimen for biomarkers study and a urine specimen for analysis will be obtained via catheterization of the patient. An analysis of the urine specimen will be completed *before* administration of the study treatment

772 773 774

775

When it has been determined that treatment may proceed, the Pharmacy should be notified to prepare and deliver the test solution. The patient will then be prepared for the treatment procedure. The patient's temperature will be recorded *before* the instillation of the test solution.

When test solution has been received from the Pharmacy, the time of preparation should be checked on the label and a determination made that the product was prepared no more than two hours ago. If the product was prepared more than two hours ago, it should be returned to the Pharmacy and fresh product obtained. Instillation of study product will be performed as described in Protocol for the Administration of Study Agent (Appendix C).

Prior to dismissal, the patient will be given instructions regarding the next study visit and will be advised of the two follow-up telephone calls as described in Section 10.3.1.1. An information sheet (Appendix F Patient Instructions Post-Treatment) will be reviewed with the patient describing signs and symptoms of complications or side effects, which should be reported, and providing 24-hour contact information. The patient will be asked to take an oral temperature at bedtime on the night of treatment and again at bedtime on the following night.

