## **B.** Subsequent Visits for Repeat Instillations:

- 1. Query patient regarding adverse effects including gross hematuria, etc.
- 2. Record patient temperature.
- 3. In the absence of adverse effects, proceed as per section I.A.1.
- 4. If adverse effects from prior therapy are ongoing, obtain voided urine specimen, assess adverse effects and manage adverse effects appropriately as per protocol and, when appropriate, at the discretion of the Principal Investigator at the site.

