#### II. Instillation of Solution

- 1. The solution is reconstituted and prepared in the pharmacy, placed in a standard blinded syringe, bagged appropriately and maintained at room temperature.
- 2. Upon transport to the clinic, the syringe is removed from pharmacy bag.
- 3. The syringe is attached to the previously placed indwelling urethral catheter.
- 4. The solution is instilled slowly over 1-2 minutes. The time of day that the instillation is performed is recorded.
- 5. If the syringe is completely (successfully) emptied into the bladder, the syringe, catheter and catheterization kit with gloves and other materials are removed together as one unit.

If the syringe cannot be completely emptied into the bladder (due to pain, severe urgency, etc., upon instillation) then the catheter and attached syringe are removed as one unit. In order to maintain strict blinding conditions, a third party (i.e. uninvolved in the study) will empty the

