**ORGANON TEKNIKA** 

#### WARNINGS

**BCG LIVE (TICE®BCG) is not a vaccine for the prevention of cancer**. BCG Vaccine, U.S.P., not TICE®BCG (BCG LIVE), should be used for the prevention of tuberculosis. For vaccination use, refer to BCG Vaccine U.S.P. prescribing information.

TICE®BCG is an infectious agent. Physicians using this product should be familiar with the literature on the prevention and treatment of BCG-related complications, and should be prepared in such emergencies to contact an infectious disease specialist with experience in treating the infectious complications of intravesical BCG. The treatment of the infectious complications of BCG requires long-term, multiple-drug antibiotic therapy. Special culture media are required for mycobacteria, and physicians administering intravesical BCG or those caring for these patients should have these media readily available.

Instillation of TICE®BCG with an actively bleeding mucosa may promote systemic BCG infection. Treatment should be postponed for at least one week following transurethral resection, biopsy, traumatic catheterization, or gross hematuria.

Deaths have been reported as a result of systemic BCG infection and sepsis.  Patients should be monitored for the presence of symptoms and signs of toxicity after each intravesical treatment. Febrile episodes with flu-like symptoms lasting more than 72 hours, fever  $\geq 103^{\circ}$  F, systemic manifestations increasing in intensity with repeated instillations, or persistent abnormalities of liver function tests suggest systemic BCG infection and may require antituberculous therapy. Local symptoms (prostatitis, epididymitis, orchitis) lasting more than 2-3 days may also suggest active infection (See Management of Serious BCG Complications subsection of Warnings).

The use of TICE®BCG may cause tuberculin sensitivity. Since this is a valuable aid in the diagnosis of tuberculosis, it is advisable to determine the tuberculin reactivity by PPD skin testing before treatment.

Intravesical instillations of BCG should be postponed during treatment with antibiotics, since antimicrobial therapy may interfere with the effectiveness of TICE®BCG (see PRECAUTIONS). TICE®BCG should not be used in individuals with concurrent infections.

Small bladder capacity has been associated with increased risk of severe local reactions and should be considered in deciding to use TICE®BCG therapy.

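### Appendix C lets staff instil through the catheter just placed with no stop for a traumatic catheterization, where the protocol's own package insert calls for a wait of at least 7 days

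*Protocol*

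**What the plan says.** Protocol Section 10.3.1 refers the instillation itself to Appendix C. Part I.A of that appendix runs in order: "Perform urethral catheterization" (step 4), dipstick for nitrites (step 5), then "If nitrites are absent, proceed with instillation" (step 6). Step 7 deals with nitrites and urine culture. Part II, step 3 continues: "The syringe is attached to the previously placed indwelling urethral catheter".

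At repeat visits, Part I.B first asks the patient about adverse effects and names gross hematuria. It then says "In the absence of adverse effects, proceed as per section I.A.1", which leads back into the I.A sequence. The other branch reads "If adverse effects from prior therapy are ongoing, obtain voided urine specimen, assess adverse effects and manage adverse effects appropriately as per protocol", with discretion left to the site investigator where appropriate.

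Appendix H, Warnings, says "Treatment should be postponed for at least one week following transurethral resection, biopsy, traumatic catheterization, or gross hematuria" and gives the reason: "Instillation of TICE®BCG with an actively bleeding mucosa may promote systemic BCG infection". Its Contraindications and Precautions each set 7 to 14 days after traumatic catheterization. For gross hematuria, the Contraindications say only to wait until it has resolved.

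**The concern.** The person at the bedside works from Appendix C. Trauma to the urethra or bladder becomes apparent when the catheter goes in, and the next stated decision is the nitrite result. If that is negative, the written direction is to go ahead, through the catheter that may have caused the bleeding.

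What is at stake is patient safety. BCG is a live organism, and the insert links instillation onto bleeding mucosa to systemic infection. Those exposed are the BCG arm in Phase 1 (130 planned in Section 13.2, up to six instillations each, so up to 130 × 6 = 780 catheterizations) and every non-responder who takes open-label BCG in Phase 2, which keeps the Phase 1 treatment schedule. Sample size, power and type I error are not involved.

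**Working it through.** The plan states no figure to reproduce. The check sets the texts side by side and then asks whether a stop would fit the schedule.

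**1. Traumatic catheterization**

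| Source | Wait before BCG |
|---|---|
| Appendix C, I.A.4–6 and II.3 | none stated |
| Appendix H, Warnings | at least 1 week |
| Appendix H, Contraindications | 7 to 14 days |
| Appendix H, Precautions | 7 to 14 days |

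The three places in the insert agree on a minimum of 7 days. Repeat visits reach the same I.A steps through I.B.3.

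**2. Other checks before dosing.** Section 10.3.1 requires a catheterized urine specimen to be analysed before treatment, and the pharmacy is notified once it is decided that treatment can go ahead. Section 10.3.1.2 carries this to Visits 2–6, and Appendix B lists a urinalysis at all six. None of these attaches a criterion for trauma or visible blood. Sections 9.2 and 11.5 set rules for antibiotics, fever and severe illness, but not for these two events.

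**3. Gross hematuria (secondary).** The insert gives two rules: until resolution (Contraindications) and at least one week afterwards (Warnings). I.B.1 asks the question and I.B.3 releases only when adverse effects are absent, which comes close to the first rule. But I.B.4 says to assess and manage and states no postponement, and bleeding that has stopped meets no wait. I.A, used at the first visit, has no hematuria question.

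Visit spacing does not supply the week. At a visit k days after the last dose, any bleeding since that dose is at most k days old. At the permitted minimum, k = 6 < 7. At k = 7, only bleeding confined to the day of the dose has reached 7 days.

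**4. Does a stop fit?** Inputs: 6 days to 3 weeks between doses and all doses within 10 weeks (70 days) of randomization (Section 10.3); first dose within 14 days of randomization (Appendix B footnote).

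- *Trauma at a repeat visit t days after the last dose, hold h days:* need t + h ≤ 21. On a weekly schedule, 7 + 7 = 14 and 7 + 14 = 21; both fit.
- *Ten-week limit, latest start:* 70 − 14 = 56 days remain. Five weekly intervals use 5 × 7 = 35, leaving 56 − 35 = 21 days of slack.
- *Hematuria ending d days after a dose:* the next dose falls on day d + 7, and d + 7 ≤ 21 gives d ≤ 14. If every interval is stretched this way from the latest start, 56 / 5 = 11.2 days per interval, so d ≤ 4.2.
- *First visit on day t after randomization:* t + 7 ≤ 14 only if t ≤ 7, so a later first visit breaks the start window. At t = 14 the first dose moves to day 21, and 70 − 21 = 49 ≥ 35, so six weekly doses still fit.

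**The case against.** The best reply is that the safeguard already exists. The insert is part of the protocol, a physician instils, Section 11.5 leaves stopping to clinical judgment, and Section 10.3.1 puts a urinalysis and a decision before the dose. Visits are scheduled by tolerability and fewer than six doses are allowed, so nobody is forced to treat on day 6.

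Much of this stands, and it rules out several stronger readings that a reader might infer:

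- *That nitrites are the only check before dosing.* They are the only stated release test in Appendix C's own sequence, but the body text adds the urinalysis and the decision.
- *That the protocol orders BCG after trauma or during bleeding.* It does not; it is silent on both.
- *That gross hematuria is ignored.* It is a named question at every repeat visit. The claim of a missing week also rests on the Warnings alone, since the Contraindications ask only for resolution.
- *That a number of affected patients can be given.* The documents have no rate of catheter trauma. The insert's hematuria table covers bladder-cancer patients on a year-long regimen, does not separate gross hematuria, and says nothing about trauma.

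What the reply does not remove is the trauma gap. An explicit instruction to proceed, with no pointer from that step to Appendix H, is a weak place to rely on memory of the insert. The protocol also writes its own holds for comparable situations, such as recent bladder biopsy (Section 6.2.3) and suspected bacteriuria (Appendix C, I.A.7).

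**Conclusion.** The point holds for traumatic catheterization: Appendix C states no wait where three places in Appendix H agree on at least 7 days, and the checks in Section 10.3.1 do not close the gap. For gross hematuria it is a clarification of lesser weight: no stated postponement while bleeding continues, and no week afterwards if the stricter insert rule is adopted.

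This is a safety gap in the working instruction that should be fixed. Its frequency is unknown. The conclusion assumes that sites follow Appendix C step by step, and that no such stop stands in pages missing from the copy read (between Appendices E and G, and just before Appendix H).

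**What to change.** Add to Appendix C after I.A.4 and in I.B.3–4, for both arms and for Phase 2:

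*If catheterization is traumatic or gross hematuria is present, do not instil. Reschedule at least 7 days after the traumatic catheterization or after the last gross hematuria (Appendix H), within the 3-week and 10-week limits; otherwise omit the dose. For the first dose only, such a hold may run past the two-week start window.*

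To apply the stricter insert rule to bleeding that has already stopped, extend the trigger to gross hematuria within the past 7 days. Using the same rule in both arms keeps it independent of allocation.

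The cost is a few lines of text and a tick-box on the existing dosing form. Some doses shift by days (7 after a traumatic catheterization), a few patients may receive fewer than six, which Section 10.3 already allows, and an occasional prepared vial is wasted. Hematuria holds may fall more often in the BCG arm, because BCG itself can cause bleeding.

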## **B.** Subsequent Visits for Repeat Instillations:

- 1. Query patient regarding adverse effects including gross hematuria, etc.
- 2. Record patient temperature.
- 3. In the absence of adverse effects, proceed as per section I.A.1.
- 4. If adverse effects from prior therapy are ongoing, obtain voided urine specimen, assess adverse effects and manage adverse effects appropriately as per protocol and, when appropriate, at the discretion of the Principal Investigator at the site.

#### II. Instillation of Solution

- 1. The solution is reconstituted and prepared in the pharmacy, placed in a standard blinded syringe, bagged appropriately and maintained at room temperature.
- 2. Upon transport to the clinic, the syringe is removed from pharmacy bag.
- 3. The syringe is attached to the previously placed indwelling urethral catheter.
- 4. The solution is instilled slowly over 1-2 minutes. The time of day that the instillation is performed is recorded.
- 5. If the syringe is completely (successfully) emptied into the bladder, the syringe, catheter and catheterization kit with gloves and other materials are removed together as one unit.

If the syringe cannot be completely emptied into the bladder (due to pain, severe urgency, etc., upon instillation) then the catheter and attached syringe are removed as one unit. In order to maintain strict blinding conditions, a third party (i.e. uninvolved in the study) will empty the

## **APPENDIX C**

## PROTOCOL FOR THE ADMINISTRATION OF BCG (cont'd.)

remaining solution within the syringe into a measuring container. This volume is recorded as per study protocol. The container, solution, and other materials are then disposed of as per section II.6.

- 6: The instillation materials are disposed of in a Biohazard container or by alternative suitable measures as determined by local/hospital regulations.
- 7: The subjects genitalia are washed with antiseptic solution.
- 8: The subject is repositioned in a comfortable manner as to maximize retention of solution. The subject may be provided with diversionary activities during dwell time while in the clinic. Antispasmodics and other agents may be administered as per protocol to maximize the subjects comfort and dwell time up to 2 hours.

#### **III** Post-Instillation

- 1. The solution is held intravesically for 2 hours. If the solution is unable to be held for 2 hours, the subject is allowed to void and the total dwell time is recorded as per study protocol.
- 2. The subject is instructed to void completely into a receptacle (toilet or "hat"). One cup (8 oz.) of bleach or equivalent is spilled into the receptacle after voiding is completed. In the absence of a "hat", the bathroom (toilet area in the clinic) is functionally closed for 15 minutes. After 15 minutes, the mixture is either flushed down the toilet or the "hat" is disposed of appropriately.
  - If the subject is unable to void at two hours from instillation, a repeat urethral catheterization is performed to empty the bladder.
- 3. The subject is given standardized instructions regarding the instillation and arrangements are finalized for the next clinic visit and follow-up phone call for the next day.

## APPENDIX D

## SYRINGE MASKING PROCEDURE

The study medication will be masked and maintained in a sterile environment until instillation. Briefly, the pharmacist will prepare the study medication appropriate for the study subject using the usual precautions and methodology approved by that institution. The final BCG suspension or saline placebo will be delivered for instillation in a masked 60 cc Luer-lock tip syringe as follows: The site pharmacist will be provided with two-part tear-off labels which will be used to affix to the syringe and to append to the CRF. The pharmacist will complete the labels appropriately after he/she has prepared the test solution instillation. The larger completed label will be affixed to the syringe before providing to the investigator or study coordinator. The smaller completed label will be appended to the appropriate CRF. The syringe mask (see draft example) will be labeled to indicate the intended recipient (by Study Number), the name or initials of the preparer, as well as the date and time of preparation. The study medications will not be instilled if more than two hours have elapsed since the time of preparation. With the sterile Luer tip cover remaining on the syringe, the backing of the mask will be peeled away and the mask pressed around the barrel of the syringe with the projections extending beyond the Luer end. The projections will then be pressed to mask the beveled portion of the syringe up to the base of the Luer-lock fitting. The sterile Luer tip cover will be removed and maintained in a sterile condition while the study medication is drawn into the syringe through an appropriate sterile needle. The needle will be removed for disposal using appropriate precautions. The sterile Luer-lock tip cover will be replaced on the syringe for transport. The syringe will be delivered with an opaque Luer-to-Catheter tip adaptor (catalog #2219: Addto, Inc., [name]). The instilling physician will remove the Luer-lock tip cover and immediately affix the adaptor. The adapter will be inserted into the instillation catheter and the instillation will proceed in the usual fashion.

## **APPENDIX E**

## Urine Specimen Collection and Archive Protocol

- 1. Urine will be collected into a sterile urine cup at 4 time points during RCT #2 (before administration of the first treatment, before and 6 hours after the 4th treatment, and at the 34 week post-treatment time point). The first two specimens will be collected by bladder catheterization; the last two will be collected by the clean catch method. Specimens should be labeled with the patient's identifier number and date of collection.
- 2. The 1st pre-treatment, 4th pre-treatment and 34 week specimens will be collected at the study sites and processed as soon as possible after collection. Urine will be centrifuged at 1000g for 10 minutes in 50 ml conical polypropylene tubes (VWR #21008-242) and the supernatant aspirated.

Fifteen (15) ml of urine supernatant will be immediately put into a sterile cup containing a stabilizing agent for the chemokine/cytokine assays. Urine is then put into a 15 ml sterile polypropylene centrifuge tube (21008-216) and a protease inhibitor tablet is then added to the tube.

Fifteen (15) ml of untreated urine supernatant will be put into a 15ml sterile polypropylene centrifuge tube (21008-216) and saved for other assays.

Urine in both of these tubes will then be aliquotted into 2ml polypropylene tubes (Continental Lab Products, San Diego, CA #3472). Each 2 ml tube will be labeled with patient's identifier number, date of collection, and whether stabilizer is present. Tubes will be frozen at -70C. Remaining urine will be discarded.

Urine cell pellets from the centrifuged urine will be re-suspended in 0.5 to 1ml of PBS. While vortexing at low speed, 2 volumes of 95% ethanol will be added to the cells, and the cell suspension then divided into two 2 ml tubes (250  $\mu$ l in one tube, 1.25 – 2.75 ml (remaining) in the other tube, and stored at –20C.

Once per month all accumulated specimens collected during these time points will be sent on dry ice by overnight mail to the following ICCTG urine banking laboratories (See Manual of Procedures for shipping addresses). One half of the aliquotted treated and untreated specimens will be sent to the University of Pennsylvania, Philadelphia, PA; one half of the aliquotted treated specimens will be sent to University of Iowa, Iowa City, Iowa. The other one half of the aliquotted untreated specimens and the small cell pellet specimens will be sent to the University of Maryland. All large cell pellet specimens will be sent to the University of Rochester, Rochester N.Y., on wet ice pack.

- 3. A clean catch urine specimen will be collected by the patient at home, 6 hours after the 4th treatment. For the 4th post-treatment specimen collection, the patient will be given a cup in which to collect the specimen, a specimen tube containing a stabilizing agent, and instructions for specimen collection. (See Appendix F Patient Instructions). The patient will then return the urine specimen to the clinical site. The clinical site will process the specimen, (See Manual of Procedures for Specimen Processing Procedure) and ship it to the University of Iowa on dry ice.
- 4. The necessary tubes and other supplies for urine collection, processing and shipping will be provided to each clinical center.

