## 10.3.1.1 Treatment Follow-up Phone Calls

The study coordinator or investigator will contact the patient by telephone on each of the two days following treatment delivery. At this time, the patient will be questioned about any side effects or adverse experiences, any medications stopped or started, and asked to report their bedtime temperature reading. Results will be recorded on the Telephone Contact During Treatment "PHNTP" CRF. If a patient cannot be reached, a message should be left, if possible, requesting that the patient call the study site.

### 10.3.1.2 Treatment Visits 2 - 6

The conduct and procedures for Visits 2-6 are the same as for Visit 1, with the exception of urine specimen for biomarkers study. A urine specimen for biomarkers study is not collected at treatment visits 2,3,5,6.

A pre-treatment catheterized urine specimen is collected at treatment visit four for biomarkers study. In addition, the patient will be instructed to collect a second urine specimen 6 hours after treatment visit four for the biomarkers study. (Appendix F-Patient Instructions Urine Collection After 4th Treatment Visit).

Each treatment visit is followed by two days of telephone follow-up. At the end of the patients last treatment visit (the 6th instillation) the patient is given a Voiding Diary to complete in the week preceding Week 18 post-treatment clinic visit.

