### Biomarker Studies

 Urine specimens for biomarker studies will be collected before the first treatment, before and after the  $4^{th}$  treatment, and at the 34 week time point. Markers to be evaluated are outlined in Section 7. The primary goal of these studies is to evaluate changes in marker levels over time and evaluate the associations between these changes and both treatment and overall patient responses. Due to the large number of markers being evaluated, in order to protect against an inflation in Type I error rates due to multiple comparisons, the sample size and power calculations below utilize an overall Type I error of  $\alpha$ =0.01. It is recognized that these evaluations are primarily exploratory, and that measures that demonstrate promise as laboratory markers may require further evaluation in another clinical trial setting.

Analyses on which sample size estimates are based will consist of two primary types. The first type will involve paired comparisons of changes from baseline to 34 weeks, within subgroups defined by treatment arm and/or response to therapy (as defined by the primary endpoint). These analyses will utilize a paired t-test. The required sample sizes to detect changes of a given magnitude, in units of standard deviations of the change (s.d.), are given in the table below. The second set of analyses will compare these changes between subgroups defined by treatment arm and/or response to therapy using a two-sample t-test. The required sample sizes to detect differences in the changes, also in units of s.d., are also in the table. These calculations assume 80% power with a two-sided  $\alpha$ =0.01

, 5												
Cina of	Required Sample Sizes											
Size of	Paired t-test to	Two-Sample t-test to Compare Two Groups										
Difference	Compare Changes	1:1 Ratio	o of Group	1:2 Ratio	of Group							
(in units of s.d.)	Within a Group	S	izes	Sizes								
1.0	15	50	(25 + 25)	57	19 + 38							
0.9	18	60	(30 + 30)	69	23 + 46							
0.8	21	76	(38 + 38)	84	28 + 56							
0.7	27	98	(49 + 49)	111	37 + 74							
0.6	36	130	(65 + 65)	147	49 + 98							
0.5	50	186	(93 + 93)	210	70 + 140							
0.4	76	> 260		> 260								
0.3	130	> 260		> 260								
0.2	> 260	> 260		> 260								
0.1	> 260	> 260		> 260								

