\* The six treatments are to be given within a ten-week period. The first instillation must occur as soon as possible after randomization, but no later than two weeks after randomization. No instillations will be given after Week 10. No more than three weeks and no less than six days may elapse between instillations. 2=At baseline and PRN. 3=Diaries to be handed out at B1 are collected at B2. Diaries collected at subsequent clinic visits will be given to the patient at the previous clinic visit. 4=When indicated. 5=Urine biomarker samples will be collected during catheterization on treatment visits 1 and 4 just before treatment. Voided samples will be collected 6 hours after the fourth treatment and at the 6-month post-treatment visit.

Page 1 of 4 05/28/02

ICCTG Protocol #2 – Visit Schedule (Weeks) Phase I – Randomized, Double-Blind Study

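### Baseline marker urine is catheterised and week-34 urine is clean catch, so the planned within-group paired t-tests of marker change cannot separate a marker change from a collection-method shift.

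*Protocol*

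**What the plan says.** **Collection.** The protocol takes marker urine at four time points: before treatment 1, before treatment 4, six hours after treatment 4, and at week 34. On method, Appendix E says: "The first two specimens will be collected by bladder catheterization; the last two will be collected by the clean catch method". The rest of the protocol agrees:

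- Section 10.3.1, treatment visit 1: "a urine specimen for biomarkers study and a urine specimen for analysis will be obtained via catheterization of the patient".
- Section 10.3.1.2, treatment visit 4: "A pre-treatment catheterized urine specimen is collected at treatment visit four for biomarkers study".
- Appendix B, footnote 5: "Urine biomarker samples will be collected during catheterization on treatment visits 1 and 4 just before treatment", and then "Voided samples will be collected 6 hours after the fourth treatment and at the 6-month post-treatment visit".

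This is a consistent design feature and not a slip in one place.

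**Analysis.** Section 13.5 (Biomarker Studies) names two main types of analysis. On the first: "The first type will involve paired comparisons of changes from baseline to 34 weeks, within subgroups defined by treatment arm and/or response to therapy"; "These analyses will utilize a paired t-test". On the second: "The second set of analyses will compare these changes between subgroups defined by treatment arm and/or response to therapy using a two-sample t-test". Both have required sample sizes tabulated at 80% power and two-sided alpha 0.01. The section describes the marker evaluations as mainly exploratory.

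The protocol provides no voided baseline specimen, no catheterised week-34 specimen, no other bridging sample, and no adjustment for collection method.

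**The concern.** A paired test of change attributes the mean within-person difference to whatever happened between the two specimens. Here two things happened to everyone: time passed (with treatment in between), and the collection route changed from catheter to void. The paired data contain no contrast that isolates either one, so a larger sample or a baseline covariate cannot help.

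If the route affects a marker, the paired test can report a change in both arms, and in responders, when the marker has not moved. If the route effect runs the other way, the test can hide a real change. Scaling by creatinine, which the pilot-data table shows for HB-EGF and IL-6, deals with dilution and not with what the route adds or removes. APF (%) and the hyperdiploid fraction are not shown on that scale.

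At stake is the second objective in Section 2, marker change over time and its relation to symptoms. Section 13.5 also foresees that promising markers may go forward to another trial.

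**Working it through.** **1. Method by time point (Appendix E; Appendix B footnote 5; Sections 10.3.1 and 10.3.1.2).**

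| Specimen | Method |
|---|---|
| Before treatment 1 (baseline) | catheter |
| Before treatment 4 (after three instillations) | catheter |
| 6 hours after treatment 4 | voided |
| Week 34 | voided |

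| Within-person contrast | Methods | Confounded? |
|---|---|---|
| Baseline to week 34 (the named paired t-test) | catheter to void | yes |
| Pre-treatment 4 to 6 hours after (not a named paired t-test) | catheter to void | yes, if it is made |
| Pre-treatment 1 to pre-treatment 4 | catheter to catheter | no |

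**2. Reproducing the plan's paired-test table.** Inputs: two-sided alpha 0.01, 80% power, change d in s.d. of the change. Power of the paired t-test is P(|T| > t), with t the 99.5th percentile of the t distribution on n - 1 degrees of freedom and T noncentral t with noncentrality d√n. Smallest n with at least 80% power:

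| d | 1.0 | 0.9 | 0.8 | 0.7 | 0.6 | 0.5 | 0.4 | 0.3 |
|---|---|---|---|---|---|---|---|---|
| Protocol | 15 | 18 | 21 | 27 | 36 | 50 | 76 | 130 |
| Recomputed | 16 | 18 | 22 | 28 | 36 | 51 | 77 | 134 |

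The normal formula gives 130 in the 0.3 row. The table reproduces closely, so the sample sizes are not at issue.

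**3. The same test when the only difference is collection method.** Let m be a pure method shift in s.d. of the change, with no true marker change. The noncentrality is m√n. Example: n = 65, m = 0.3 gives 0.3 × √65 = 2.42 against a critical value of 2.655, so the rejection probability is 0.41. The protocol does not give m; the range is an assumption.

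| n | m = 0 | 0.2 | 0.3 | 0.4 |
|---|---|---|---|---|
| 32 (smaller group in the pilot-data table) | 1% | 7% | 17% | 33% |
| 65 (group size in the marker examples) | 1% | 16% | 41% | 71% |
| 130 (full arm, no loss) | 1% | 37% | 79% | 97% |

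**4. The opposite error.** With a true change of 0.5 s.d. at n = 65, power is 91%. A method shift of -0.2 leaves a net 0.3 s.d. and 41% power. A shift of -0.3 leaves a net 0.2 s.d. and 16%.

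**5. Between-arm comparison.** Mean change is (effect of BCG + time + m) in one arm and (effect of saline + time + m) in the other. If m is the same in both, it cancels. A simulation of 20,000 trials with 65 per arm and no arm effect gave rejection rates at alpha 0.01 of 1.0% (m = 0), 1.0% (m = 0.3) and 0.9% (m = 0.5). For responders against non-responders the same cancellation holds only if m is unrelated to response, because response is not randomised.

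**6. Baseline as covariate.** With residual variances compared at equal baseline and week-34 s.d. and correlation ρ, ANCOVA has variance σ²(1 - ρ²) and the change score 2σ²(1 - ρ). The ratio is (1 + ρ)/2: 0.65, 0.75 and 0.85 for ρ = 0.3, 0.5 and 0.7. If the two collection methods give different s.d.s, σ0 and σ1, the variances are σ1²(1 - ρ²) and σ1² + σ0² - 2ρσ0σ1. The second exceeds the first by (σ0 - ρσ1)², which is never negative.

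**The case against.** **No shift is shown.** The rejection probabilities are a t-test's power curve at assumed shifts. The protocol reports no catheter-against-void difference for any marker, and if there is none the paired test keeps its 1% level. This stands: the defect is that the design cannot tell the two apart, not that a bias of known size exists.

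**Not every before-and-after contrast is affected.** A reader might infer that all within-group marker changes are lost. The documents do not support that. The visit-4 pre-treatment specimen is catheterised and follows three instillations, so the change from visit 1 is like for like. The six-hour contrast has the mismatch, but Section 13.5 does not name it as a paired t-test.

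**Nor are the marker results as a whole invalid.** The second planned analysis already compares changes between arms, where a common shift cancels. ANCOVA adds precision and does not itself remove the shift; randomisation does that.

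**A full arm of 130 flatters the problem.** It assumes no loss, while Section 13.4 allows for up to 15% withdrawal and the marker examples use 65. This is fair, so the figures at 65 and 32 carry the point. The inflation remains at both.

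**The trial's size does not rest on these tests.** Section 13.2 derives the 260 participants from the primary endpoint; Section 13.5 only tabulates marker sample sizes.

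**Exploratory status.** The protocol says these evaluations are mainly exploratory and may need another trial. That lowers the severity but does not make an unidentifiable contrast interpretable.

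**Conclusion.** The point holds for the within-subgroup paired t-tests of baseline-to-week-34 marker change: collection method and time are completely confounded in every participant, and nothing in the protocol separates them. A comparison of the visit-4 pre-treatment and six-hour specimens would share the fault. The visit-1 to visit-4 pre-treatment change does not.

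The size depends on a method effect that the protocol does not give. Over an assumed 0.2 to 0.4 s.d. of the change, the nominal 1% error becomes 16% to 71% at 65 per group and 7% to 33% at 32. These figures assume normally distributed changes. The between-arm comparison is sound if the shift is equal in both arms. The responder comparison is sound only if the shift is unrelated to response.

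The severity is modest. The primary endpoint and the symptom endpoints are not touched, and the marker analyses are declared mainly exploratory.

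**What to change.** Change the wording of Section 13.5 (Biomarker Studies):

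1. State that baseline and week-34 specimens differ in collection method, and that within-group baseline-to-week-34 paired t-tests will not be used as evidence of marker change.
2. Base week-34 marker inference on the randomised between-arm comparison of the week-34 level, with the baseline marker as covariate (ANCOVA).
3. Use the catheter-to-catheter pair, visit 1 to visit 4 before treatment, for within-group on-treatment change.
4. State that responder against non-responder comparisons assume a method effect unrelated to response.

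This needs no new specimens. The cost is that no within-arm change can be claimed at week 34.

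Adding a voided specimen just before the visit-1 catheterisation may look like an easy bridge, but it is not recommended. Appendix E needs 30 ml of supernatant (two portions of 15 ml) plus a cell pellet, Section 10.3.1 needs a catheter specimen for urinalysis as well, and eligibility requires only one void of at least 75 cc in 24 hours. Voiding first could deplete the catheter specimen on which the one like-for-like contrast depends.
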